#### 12.34 Posterior Fossa Boost

The posterior fossa boost will be a conformal limited target volume boost. 3D-based treatment planning is mandatory for these volumes. The Gross Target Volume (GTV) is based upon the T1 weighted MRI with and without Gadolinium contrast. Identification of the GTV shall be based upon pre-operative extent and anatomic shifts or changes after surgery. The GTV should include any residual enhancing tumor mass and the wall of the resection cavity. The Clinical Target Volume (CTV) is defined as the GTV plus a 1.5-cm margin except at bone or tentorial interface (where it remains within the confines of the posterior fossa). The Planning Target Volume (PTV) margin should be an additional 0.3 to 0.5 cm around the CTV, depending on the setup error of the treatment modality used. In treatment planning, shielding of critical structures should be attempted. At least 95% of the prescribed study dose (55.8 Gy) must encompass at least 95% of the PTV as shown by DVH. No part of the PTV should receive less than 50 Gy.

### 12.35 Supratentorial Boost

The treatment volume for a supratentorial boost will be defined using a 1 cm margin around the presurgical MRI defined tumor volume. In the event of proximity to normal tissue structures, this margin may be reduced to 0.5 cm to allow for shielding of critical structures. If the margins are reduced to 0.5 cm, this should be clearly stated and justified in the submitted QA documentation. As the total dose to the optic chiasm and both optic nerves should not exceed 50.4 Gy, these structures should be blocked accordingly. A supratentorial boost set up to treat metastatic disease (M2) should meet the same guidelines as that for a boost for a primary supratentorial tumor.

### 12.36 Spinal Boost(s)

For patients with spinal deposits of disease, focal boosts to the pre-chemotherapy volume with 1cm margin (target volume) will be employed.

## **12.4 Three Dimensional Treatment Planning**

Three dimensional (3D) treatment planning will be used for the whole brain and spinal axis treatments as well as any boosts.

### 12.41 Planning System Requirements

Any volume based treatment system e.g., conformal radiation treatments (co-planar or non-coplanar), stereotactic radiotherapy, intensity modulated radiotherapy, and proton therapy, is allowable if it satisfies the following criteria. Brachytherapy and stereotactic radiosurgery are not allowable.

### 12.42 Treatment Planning

Radiotherapy treatment planning will be based upon contrast-enhanced CT or MRI scan. This scan should be performed in the axial plane at a spacing of no more than 3mm. The scan should encompass the entire cranium and the cervical spine down to the level of at least C3.

#### 12.43 Normal Tissue Volumes

The following normal tissue will be defined on the treatment planning scan, and dose-volume histogram data will be reviewed for these structures:

- 1) L, R Cochlear and vestibular apparatus bilaterally
- 2) Supratentorial brain
- 3) Pituitary gland
- 4) L, R Optic nerves and chiasm

#### 12.44 Dose Prescription

The radiation dose will be calculated and normalized to the isocenter of the beams used for treatment. The 95% isodose surface will be required to completely encompass the PTV.

### **12.5 Treatment Dose**

#### 12.51 Dose Definition

##### 12.511 Absorbed Dose Specification

All doses shall be specified as cGy to water.

##### 12.512 Tissue Inhomogeneity Consideration

Inhomogeneity correction should be made for bone and lung transmission.

#### 12.52 Prescription Point

##### 12.521 Brain

If the brain is treated by parallel-opposed fields, the dose should be defined at a point along the central axis midway between the lateral entrance points (midplane). If an independent jaw or half-beam block technique is used, the dose should be specified at an off-axis point that corresponds to the midplane point used for a conventional "opposed lateral" treatment set-up.

##### 12.522 Spine

The dose to the spine should be prescribed along the central axis at a depth representing the posterior margin of the vertebral bodies as determined by cross-table lateral x-rays, MRI or CT scans.

#### 12.523 Primary Site Boost

For 2D treatment plans the prescription point should be in the center of the target volume, i.e. along the central axis of the opposed beams, midway between the two entrance points. Note that the dose contribution to the posterior fossa dose from the whole brain fields should be considered equal to the dose prescribed to the whole brain. Correction for decreased separation should not be made. For 3D treatment plans, the prescription point should be as defined in Section 12.45.

#### 12.524 Other Boost Sites

The dose to other boost sites will be calculated at the mid-tumor point calculated on the central axis of the boost fields.

### 12.53 Total Treatment Dose

#### 12.531 Craniospinal Axis

All patients will receive 23.4 Gy to the craniospinal axis.

#### 12.532 Primary Site Boost

All patients with primary tumor in the posterior fossa will receive a boost of 32.4 Gy to the posterior fossa. All patients with a supratentorial primary tumor will receive a boost 32.4 Gy to the volume described in section 12.3. As noted there, the total dose to the optic chiasm and both optic nerves should be limited to 50.4 Gy. In addition, if the boost volume occupies more than 2/3 of the supratentorial compartment, the boost dose should be limited to 27 Gy.

#### 12.533 Metastatic Site Boost

Patients with M1 disease will receive no additional boost. Patients with M2 disease (intracranial subarachnoid disease) will receive boosts of 32.4 Gy to focal areas of supratentorial or posterior fossa metastatic disease. If the volume of a boost to the supratentorial compartment exceeds 2/3 of the

supratentorial compartment volume, the boost will be limited to 27 Gy. The boost dose to the optic chiasm and both optic nerves must be limited to 27 Gy. 3D treatment planning may be used for boosting M2 disease. If 3D planning is used, definitions boost volumes for M2 disease will be the same as specified for boosts to the primary tumor. Patients with M3 disease (spinal deposits of disease) are subdivided into those with diffuse disease and those with focal disease. Diffuse spinal disease is defined as radiographically visible multiple sites of disease in each of at least 3 out of 4 spinal regions (i.e., cervical, thoracic, lumbar or sacral).

If there is diffuse involvement of the spine, the entire spine will be treated to 23.4 Gy. An MRI scan of the spine should be performed when the spine has received 23.4 Gy, and areas of visible disease remaining at that point should be boosted to 45 Gy when above the termination of the spinal cord and 50.4 Gy when below the termination of the cord. If there are focal areas of spinal deposits which do not meet the definition of diffuse involvement defined above, the entire spine will be treated to 23.4 Gy. The focal areas of tumor seen on the initial spinal MRI will be boosted to 45 Gy. Focal deposits below the termination of the cord as defined by the initial MRI will be boosted to 50.4 Gy. The margin for boosting metastatic deposits will be at least 7 mm, and preferably 10 mm.

#### 12.54 Time Dose Consideration

##### 12.541 Daily Dose

The daily dose to the prescription points should be 180 cGy. Corrections for a higher contribution of dose to the PF or upper cervical spinal cord from whole brain treatment should not be made.

##### 12.542 Fractionation

All radiation fields should be treated once each day and treatments should be given 5 days per week.

##### 12.543 Unplanned Treatment Breaks

Interruption or discontinuation of radiation will be permitted ONLY for:

1) Severe medical conditions precluding delivery of radiation. This does not include straightforward fever and neutropenia admissions (i.e. radiation therapy and carboplatin should continue to be administered without interruption). If radiation cannot be resumed within two weeks of discontinuation, the study chair should be informed and the patient will be off study.

2) Hematologic toxicity alone should NOT result in unplanned treatment breaks.

Only when the patient is clinically unstable, should radiation therapy be held.

ONCE CRANIOSPINAL RADIATION THERAPY IS STARTED, IT IS TO BE COMPLETED WITHOUT INTERRUPTION (I.E. BOOST RADIATION SHOULD NOT BE ADMINISTERED INSTEAD OF CRANIOSPINAL RADIATION UNTIL COUNTS RECOVER).

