## **9.0 CRITERIA FOR REMOVAL FROM PROTOCOL THERAPY, FOLLOW-UP, AND OFF STUDY CRITERIA**

### **9.1 Criteria for Removal from Protocol Therapy**

Patients may be removed from protocol therapy prior to completion under the following circumstances:

- a) Disease relapse/progression (see Section 8.0)
- b) Parent/patient request
- c) Death
- d) Physician or investigator's discretion

Discontinuation for other reasons will be considered protocol deviations.

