### **9.2 Removal from Protocol Follow-up**

Patients may be removed from protocol specified follow-up under the following circumstances:

- a) Death
- b) Parent/patient request
- c) Entry onto a sanctioned second line therapeutic study or follow-up study.

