### **13.33 Analysis of Efficacy**

If there are 1 or fewer deaths from tumor progression, within 10 patients, with 3 years median follow up, then a presumption can be made that the reduction in radiation dose has not led to a decline in efficacy. The information would then be supplied to the national group (Children's Oncology Group) as a potential next national Phase III, randomized study.

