## **13.4 Interim Monitoring**

### **13.41 Interim Monitoring of Treatment Efficacy**

Because of the short duration of this study, therapeutic efficacy as measured by either EFS or survival, will not be subject to interim monitoring. The first formal analysis of this study will occur when median follow-up is approximately 18 months. The formal early monitoring of dose limiting toxicities and any toxic deaths will provide early warning of significant safety problems.

Because we expect a survival of approximately 90%, if there is one failure in ten patients, we will accept that as equivalent. If there are 2 deaths from tumor progression within the first 10 patients, the study will be closed. All patients will subsequently be monitored. If there are no further deaths and the number of patients is still less than 10, the study will be re-opened to accumulate a total of 10 patients. The expectation is that there will be no toxic deaths. Any toxic deaths will result in the suspension of the study, investigation into the cause of death, and discussion with the IRB.

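### The off-study rule in 12.543 conflicts with 9.2, and 9.2(c) lets follow-up stop before the event counted in 13.33, so progression deaths could go uncounted among ten patients

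*Protocol*

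**What the plan says.** Four parts of the protocol bear on this point.

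- **12.543 (Unplanned Treatment Breaks).** When a severe medical condition interrupts radiation and it cannot be resumed within two weeks, "the study chair should be informed and the patient will be off study". The wording is mandatory and refers to the study, not to protocol therapy.
- **Section 9.** Its title announces off-study criteria, but it contains only 9.1 (removal from therapy) and 9.2 (removal from follow-up). Section 9.1 does not name a radiation break, although its item on physician or investigator discretion could cover one. It closes with "Discontinuation for other reasons will be considered protocol deviations". Section 9.2 opens with "Patients may be removed from protocol specified follow-up under the following circumstances" and lists three: death, parent or patient request, and "Entry onto a sanctioned second line therapeutic study or follow-up study". A radiation break is not among them.
- **13.33 (Analysis of Efficacy).** The condition for presuming that the lower radiation dose has cost no efficacy is "If there are 1 or fewer deaths from tumor progression, within 10 patients, with 3 years median follow up".
- **13.41 (Interim Monitoring).** The threshold is explained by "Because we expect a survival of approximately 90%, if there is one failure in ten patients, we will accept that as equivalent", and the closing rule is "If there are 2 deaths from tumor progression within the first 10 patients, the study will be closed".

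No section says whether a patient who goes off study under 12.543 remains one of the ten. None requires vital status to be collected after that exit or after entry to a second-line study.

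**The concern.** Two exits can come before the event that decides the trial. Under 12.543 a patient leaves the study because of a severe medical condition. Under 9.2(c) a patient may leave follow-up on entering a second-line study, which usually means the tumour has already relapsed. In the second case the patient has a raised risk of the counted event, death from tumour progression, and may leave observation before it happens.

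If such deaths are not seen, or the patients are not counted, the tally can only fall. The error therefore runs one way, toward presuming no loss of efficacy. The threshold separates one death from two, so a single uncounted death can turn a closed study into one that is passed to the national group as a candidate for a Phase III trial.

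**Working it through.** **Inputs from the protocol.** Ten patients (13.1). Success with at most one death from tumour progression (13.33). Closure at two such deaths (13.41). Expected survival of about 90% (13.41).

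**Inputs assumed.** The protocol gives no unacceptable death rate and no rate of loss. I take true progression-death rates p of 20% and 30% by the time of analysis, independent patients, and a share q of those deaths that goes unseen, set at 10%, 25% and 50%.

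**Step 1: the plan's own figure.** Expected failures are 10 × (1 − 0.90) = 1, which matches the one failure accepted in 13.41. No error rate or power is stated, so there is nothing further to reproduce.

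**Step 2: chance of passing with every death seen.** P(pass) = (1 − p)^10 + 10 p (1 − p)^9.

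- p = 0.20: 0.107 + 0.268 = 0.376 (from unrounded terms)
- p = 0.30: 0.028 + 0.121 = 0.149

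**Step 3: a share of the deaths unseen, denominator kept at ten.** The observed death rate becomes p(1 − q), entered in the same formula.

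| True rate p | q = 0 | q = 10% | q = 25% | q = 50% |
|---|---|---|---|---|
| 20% (observed 20, 18, 15, 10%) | 0.376 | 0.439 | 0.544 | 0.736 |
| 30% (observed 30, 27, 22.5, 15%) | 0.149 | 0.202 | 0.305 | 0.544 |

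**Step 4: one patient who would have died is dropped from the ten.** If that patient is kept and the death counted, the rule is passed only when the other nine have no progression death: (1 − p)^9. If the patient is dropped, the rule is passed when the other nine have at most one: (1 − p)^9 + 9 p (1 − p)^8.

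| True rate p among the other nine | Kept and counted | Dropped |
|---|---|---|
| 20% | 0.134 | 0.436 |
| 30% | 0.040 | 0.196 |

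The comparator must be the nine-patient figure in the middle column. Setting 0.436 against 0.376, or 0.196 against 0.149, would describe the removal of an average patient and would understate the effect of removing one who would have died.

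**Step 5: the sections side by side.** Under 9.2 alone, a patient with a long radiation break stays in follow-up, because the break is not on the list. Under 12.543 the same patient is off study. Both cannot govern. Under 9.2(c) there is no conflict between sections, but follow-up may stop between progression and death, while 13.33 and 13.41 count only the death.

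**The case against.** Several fair points can be made for the plan.

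- **Removal is permitted, not required.** Section 9.2 uses permissive wording and concerns protocol-specified follow-up, which most naturally means the scheduled examinations and scans of 6.4 and 6.5. A reader might infer that follow-up must end and that failures are certain to disappear. The text does not say so. Deaths could be missed; it is not established that they will be.
- **A radiation break is not a tumour event.** Section 12.543 concerns severe medical conditions. A reader might infer that these patients are likely tumour failures, but the protocol does not say that. Likewise, 9.2(c) covers follow-up studies, which imply no relapse.
- **9.2 could be read as protecting these patients.** If it governs, follow-up continues after a radiation break and nothing is lost. That is correct, but it depends on which section prevails, and the protocol does not settle this.
- **Event-free survival is largely intact.** A patient entering second-line treatment has normally progressed, so the event defined in 13.31 is already recorded. This stands. A reader might infer that the event-free survival estimate is biased by the same route; for events recorded before second-line entry it is not. The exposure lies in the death count of 13.33 and 13.41.
- **Later deaths may be known anyway.** Section 14.2 has disease deaths reported at continuing review. That is reporting to the ethics board. It suggests that such deaths are expected to become known, but it does not secure follow-up of a patient who has left.
- **The analysis population may be set in the SAP.** It may. But an SAP cannot restore vital status that the protocol allowed not to be collected.

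**Conclusion.** The point holds in a limited form. Sections 12.543 and 9.2 disagree on whether a patient with a long radiation break is still followed, and they must be reconciled. Separately, 9.2(c) allows follow-up to stop ahead of the event on which the success and closing rules depend. Together these rules could lower the death count and bias the decision toward no decline.

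The size depends on loss shares that the protocol does not give. At 10% of deaths unseen the shift is modest: 0.063 at a true 20% rate (0.439 − 0.376) and 0.053 at 30% (0.202 − 0.149). The 50% case is the extreme of the range and should not be quoted alone. For a single dropped patient who would have died, the chance of passing rises by 0.302 at 20% (0.436 − 0.134) and by 0.156 at 30% (0.196 − 0.040). All figures assume independent patients with a common death rate, apart from the one fixed as a failure in Step 4.

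**What to change.** 1. Reconcile 12.543 with Section 9 by separating *off protocol therapy* from *off study*, and supply the off-study criteria that the title of Section 9 announces. The two-week radiation rule itself is not in question and need not change.
2. State in 9.2 and 13.33 that all enrolled patients stay in the denominator and are followed for progression and vital status to the 3-year analysis, including after stopping radiation or entering a second-line study, unless consent is withdrawn.

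The cost is a protocol wording change and continued vital-status contact for a few patients.

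Counting progression as well as death as a failure in 13.33 and 13.41, in line with the event-free survival objective, would further limit what can be lost. It answers a separate defect, the mismatch between the endpoint and the decision rule, and does not replace the two changes above.

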#### 12.55 Dose Homogeneity and Reference Points

##### 12.551 Brain, Posterior Fossa and Supratentorial Boost

Throughout the central plane, a dose homogeneity of +5% relative to the prescription point is required. A correction for the higher contribution of dose to the PF and upper cervical spinal cord from whole brain treatment is not required. In no instance will homogeneity exceeding 10% in the central plane be acceptable.

##### 12.552 Spine

The maximum dose variation along the longitudinal axis of the spinal cord should be +5%. Tissue compensations may be required to achieve this degree of dose uniformity. The dose to the spinal cord at the level of T2 and L3 should be recorded as off-axis points.

##### 12.553 Uniformity Reference Points:

The reference point for the posterior fossa due to the whole brain radiation will be the midplane of the skull at a point that will be along the central axis of the lateral posterior fossa boost points. The posterior margin of the vertebral body representing the anterior margin of the spinal canal will

represent the spinal cord uniformity reference point. The off-axis reference dose will be calculated at the anterior margin of the spinal canal at T2 and L3. The midplane of the cranium will be used as the uniformity reference point for the cranium.

#### 12.554 Allowed Methods of Dose Compensation

To remain within the acceptable range of uniformity, the areas receiving higher dose may be blocked for the last few fractions of treatment. Wedges or tissue compensators may be used at the discretion of the individual radiation oncologist.

### 12.6 Treatment Technique

#### 12.61 Patient Position

For cranio-spinal irradiation the patient should be treated prone. The neck should be extended sufficiently to keep the mandible out of the exit beam of the spinal field but not so much as to exceed the dose uniformity specifications of the spinal field. Immobilization devices such as head holders or custom molds are required for 3D treatment plans. For boosting the posterior fossa or supratentorial sites, the patient may be in either the prone or supine position.

#### 12.62 Whole Brain Irradiation

Parallel-opposed fields may be used. Alternatively, the field center can be placed near the match line with the spinal field and an independent jaw or half-beam block technique utilized. This method decreases overlap at the match line. The collimation of the brain field should be rotated to match the divergence of the spinal field according to the equation:

$$\text{Collimator angle} = \tan^{-1} \left( \frac{\text{spine length}/2}{\text{Source-to-axis distance}} \right)$$

The lateral fields may be angled posteriorly to spare the collateral lens, but, if this is done, great care must be taken to assure adequate coverage of the cribriform plate. Custom divergent blocking of at

least 5 HVL should be used to shape the brain field at the base of the skull and around the eyes. The brain field should extend to at least 1 cm beyond the periphery of the scalp.

#### 12.63 Spinal Cord

Preferably, the spinal volume should be treated with a single posterior field. An extended SSD is preferable to the use of adjacent ports. If adjacent ports are necessary, the 50% decrement should cross at the posterior margins of the vertebral body. It is preferable that the match line be placed inferior to the spinal cord (below L2) and should be moved every 900 cGy. Custom blocking may be required at the inferior border of the spine. An attempt should be made to avoid exit through the jaw and mouth from the spinal field by hyperextending the neck, if the curvature does not compromise dose homogeneity.

#### 12.64 Abutting Fields

With the use of collimator rotation and an independent jaw technique, the cranial and spinal fields may be directly abutted (light fields). Many radiation oncologists, though, are more comfortable with a gap between the cranial and spinal light fields. A gap of 0.5 cm is allowed on this protocol. The match line should be moved three times during treatment of the cranio-spinal axis. Also, a penumbra broadening "match line wedge" or a dynamic wedge may be used. The match line should never overlap the posterior fossa boost. Therefore, it is recommended that the first match line lie just above the shoulder, and the last 3-cm higher. Alternatively, the first match point could begin at the superior point and end at the inferior point.

#### 12.65 Primary Site Boost

For patients treated with posterior fossa primary sites, the primary site boost should be treated by a pair of opposed lateral fields. For patients with supratentorial primary sites, or patients planned with 3D techniques, any appropriate configuration of fields is allowable.

